4. DATA ANALYSIS PLAN

Once the preliminary analyses for the detection of possible errors in the recording of the data have been made, exploratory and descriptive analyses will be carried out to study the distribution of the variables and the presence of atypical values. The applied inferential statistics will be in accordance with the characteristics of the data obtained (distribution

of the data, qualitative/quantitative nature of the data, etc.) and with the hypotheses proposed in the study. Models of repeated measures two-way ANOVA will be performed, using as dependent variables (DV):

- For objective 1, the change in the BMI between the four moments of assessment [pre (session 1), post-treatment (session 7), 3-month follow-up and 6-month follow-up];
- For objective 2: quantity, type and calories of the food intake; quantity of physical activity; degree of adherence to the diet and physical exercise recommendations; waist circumference and waist to hip ratio; food decision-making and valuation.
- For objective 3: approach-avoidance bias, inhibitory control, food choice task and food liking task will be used to assess the impulsive system; delay discounting and frequency and quantity of food and physical exercise behaviors will be used to assess the executive system. Furthermore, differences on BMI, food behaviors and physical exercise between the groups will be performed to compare the impulsive training and the reflexive training.

Effect sizes for between-group pairwise comparisons will be calculated using the following equation by Morris (2008) to estimate the magnitude of the difference between two groups at two different points in time:

$$d = c_p \left(\frac{(M_{TIME 2, GROUP 2} - M_{TIME 1, GROUP 2}) - (M_{TIME 2, GROUP 1} - M_{TIME 1, GROUP 1})}{SD_{TIME 1}} \right)$$

where M is the mean for each situation, and $SD_{TIME 1}$ refers to the pooled standard deviation of the first measurement moment:

$$SD_{TIME 1} = \sqrt{\frac{(n_{GROUP 2} - 1)SD_{TIME 1, GROUP 2}^2 + (n_{GROUP 1} - 1)SD_{TIME 1, GROUP 1}^2}{n_{GROUP 2} + n_{GROUP 1} - 2}}$$

and c_p is a correction for bias, calculated by:

$$c_p = 1 - \frac{3}{4(n_{GROUP 2} + n_{GROUP 1} - 2) - 1}$$

where n is the sample size for the corresponding group.

Within-group effect sizes will be calculated using Cohen's d (Cohen, 1992):

$$d = \frac{M_{TIME 2} - M_{TIME 1}}{SD_{pooled}}$$

where SD_{pooled} is:

$$SD_{pooled} = \sqrt{\frac{SD_{TIME 1}^2 + SD_{TIME 2}^2}{2}}$$

[figure not shown]
Based on Cohen's (1992) rule of thumb, clinical significance of change will be reflected by medium within-group effect sizes ($d \geq .5$).

Mediation and/or moderation analysis will be carried out to study the role of variables related to cognition, affect, stress and non-homeostatic food intake, motivation and personality on the program outcome measures.

In addition, possible differences in the program outcomes will be assessed based on sex and weight classification (overweight and obesity -type I and type II).

All the analyses described will be carried out following an intention to treat strategy (ITT) and analysis per protocol (PP). Corrections will always be considered to control for multiple comparisons.

- For objective 4, the average cost and effectiveness (BMI and QALY) for the 3 groups (intervention, sham and treatment as usual) will be estimated. The ratios of incremental cost effectiveness and incremental utility cost will be calculated as the cost and effectiveness difference (BMI and QALY) for the 3 groups. All the analyses will be carried out according to the methodological recommendations for Spain (López-Bastida et al., 2010). The perspective of the health system will be used, including only direct costs. The uncertainty of the results will be carried out through various deterministic sensitivity analysis (AS) and a probabilistic one using nonparametric bootstrapping methods of 1000 iterations (Luce et al., 2001) that will allow to represent the cost-effectiveness plane and the Acceptability curve. The AIP will estimate the variation that the introduction of neurocognitive training would imply for the budget of the public health system, based on the estimated costs of the alternatives compared and the estimated number of patients expected to benefit from the program. Likewise, univariate and multivariate AS will be performed to analyze different budgetary scenarios based on a possible variation in the cost variables and number of beneficiary patients.

**Only in experimental and active control groups (what is not in italics is done by all three groups: experimental, active control, and control) //* Assessment task

Figure 1: Procedure of the program.

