2. METHODOLOGY

2.1. Design: Randomized controlled trial of parallel groups.

2.2. Participants:

Sample size and statistical power:

The calculation of the sample size has been made from Objective 1, which focuses on detecting a clinically significant difference in BMI that is the primary outcome measure. Based on previous work that explored weight change in follow-ups after the application of neurocognitive training in people with overweight and obesity (Bazzaz et al., 2017, Kakuschke et al., 2018, Sze et al., 2015), we have selected the smaller sample size (Cohen's $d = 0.46$). With this data, considering the statistical method (models of repeated measures inter and intra subjects), the number of groups ($g = 3$), and assuming an alpha level of 0.05 and a power of 0.80, the resulting sample size calculated with G-Power was 105 participants. To date, no study has conducted a program based on the combination of different neurocognitive tasks that have been proposed as effective for the treatment of obesity, with a 6-month follow-up period. Thus, we opted for a conservative estimate increasing the number of participants to 150. Then, the study could suffer a sample loss of 30% from the initial session to the follow-up at 6 months and the statistical power would be still guaranteed. Previous studies that explored neurocognitive training to lose weight with different follow-up periods have showed smaller attrition rates [i.e., 16% in a 3-month follow up (Carbine et al., 2021); 12.3% in a 2-month follow-up (Forman et al., 2019); 3.4% in a 6-month follow-up (Lawrence et al., 2015)].

Participants:

The participants ($N=150$) will be randomly allocated to three groups: experimental group (neurocognitive intervention; $n=50$), active control group (sham intervention; $n=50$), and control group (treatment as usual; $n=50$).

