2.4. Outcome measures:

Note: The measures have been selected attending to ADOPT (Accumulating Data to Optimally Predict Obesity Treatment), to generate evidence about the efficacy for obesity interventions (MacLean et al., 2018). These measures are marked with an asterisk (*).

(1) Main outcome measure

- a. BMI*: Height and weight will be measured to determine BMI. The weight and height for the calculation of the BMI (kg/m²) will be obtained with a pharmacy digital scale

BMI will check for the results of the whole program (the 4 intervention sessions), and will be registered weekly from session 1 to post-treatment assessment, and will be also registered at follow-ups (3- and 6-months post-treatment). In addition, the week before the pre-treatment assessment session, it will be recorded daily to obtain the baseline weight and then averaged.

(2) Secondary outcomes (changes in cognitive measures, changes in eating and physical exercise behaviors and body measures).

(2.1) Changes in cognitive measures.

- a. Approach-avoidance bias: The approach-avoidance bias will be calculated before and after the 1-week training with the Tilt Task app. Participants should zoom in or out the appetizing and healthy food images that appear on the screen, depending on the presentation format of the image (horizontal or vertical). Approach and avoidance trials will be 50% for each type of image (healthy vs. unhealthy). The average reaction time of the approach (pull) and avoidance (push) trials will be subtracted separately for healthy and unhealthy foods, with the positive and

negative scores representing approximation and avoidance bias, respectively (see Kakuschke et al., 2018 for a full description).

- b. Food inhibition assessment: Using the Food Trainer task, reaction time for the high-calorie and low-calorie foods paired 50% with the go and 50% with the no-go signal will be measured before and after the 1-week training with the app. The average response time for go and no-go items will be calculated according to the type of images (appetizing and healthy foods), and commission errors will be recorded (see Lawrence et al., 2015).

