3. PROCEDURE

All assessments and intervention sessions will be delivered online. Inclusion and exclusion criteria will be checked through the data collected in a questionnaire of sociodemographic and clinical variables. Further, psychopathology exclusion criteria will be tested with two questionnaires to measure depression, anxiety, and stress symptoms as

well as binge eating and bulimia (DASS-21 and QEWP-5), and a short clinical interview by phone and/or information requested by email in those cases where there are doubts about any of the aspects collected through the online instruments.

All candidates who meet the criteria will attend an information meeting about the project in which they will receive written and oral information, and will be asked for their informed consent. Then, participants will be randomly assigned to groups before the pre-treatment assessment sessions. The three groups of the study (intervention, active control and control) will complete all of the evaluations, as well as the follow-ups (see below and Figure 1). Further, all groups will receive the pre-treatment interventions (Motivational Interviewing, nutrition and physical activity sessions). What will differentiate the groups will be, therefore, the treatment: neurocognitive intervention vs. sham vs. usual treatment. The control groups will be offered the treatment sessions (without the assessment components) after the end of the 6-month follow-up.

Sessions will be developed in groups of 5-6 persons. If a participant misses a session he/she can attend another one within 3-4 days. There will be 10 experimental groups of active training = 50 participants; 10 active control groups of sham training = 50 participants; and 10 control groups = 50 participants. The program will comprise 8 weeks including three assessments (pre, intermediate and post-treatment), four intervention sessions, as well as pre-treatment and post-treatment intervention sessions. Also, two follow-up sessions at 3 and 6 months after treatment (see below). Sessions will last about 1 hour and a half.

Sessions will consist of the following (see Figure 1):

1. Informative session (session 1; week 0): All participants will be informed about the aims and the procedure of the research, and they will provide written informed consent.

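### ITT is promised for the BMI analysis, but no ITT set or missing-data method is defined, and the repeated-measures ANOVA named for it would in its standard form drop anyone missing one of four values

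*Combined protocol and SAP*

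**What the plan says.** Section 4 (Data analysis plan) gives the model: "Models of repeated measures two-way ANOVA will be performed, using as dependent variables (DV". For objective 1 the variable is BMI at four moments: "pre (session 1), post-treatment (session 7), 3-month follow-up and 6-month follow-up". The same section later states: "All the analyses described will be carried out following an intention to treat strategy (ITT) and analysis per protocol (PP". It defines neither set. Nowhere do the documents name imputation or a likelihood-based method, state an assumption about why data are missing, or plan a sensitivity analysis for missing BMI. The only sensitivity analyses described belong to the economic evaluation.

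Section 2.2 (sample size) treats loss to follow-up as a matter of power. The study could bear "a sample loss of 30% from the initial session to the follow-up at 6 months and the statistical power would be still guaranteed". It adds: "Previous studies that explored neurocognitive training to lose weight with different follow-up periods have showed smaller attrition rates", citing 16% at 3 months, 12.3% at 2 months and 3.4% at 6 months.

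Section 2.4 plans more BMI values than the four analysed under objective 1. BMI "will be registered weekly from session 1 to post-treatment assessment, and will be also registered at follow-ups". Section 3 also lists BMI at the week-5 intermediate assessment.

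**The concern.** ITT needs two things that the plan omits: a statement of who is in the set, and a rule for participants whose outcome is partly missing. A standard repeated-measures ANOVA supplies a rule silently, by deleting every participant with a gap. The primary result could then be reported as ITT while resting on completers.

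Three things are at stake:
- **Precision.** Someone who attends up to the 3-month visit and misses the last one contributes nothing to objective 1.
- **Bias.** Completers may differ from those who leave.
- **Pre-specification.** If handling is left open, it can be chosen after the data are seen. Section 4 says the statistics will suit the data, but its examples are distribution and type of variable, not missingness.

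The missing definition has a practical edge. Section 3 randomises participants before the pre-treatment assessment, so someone could be randomised and leave before a full baseline is recorded. Nothing says whether that person is in the ITT set.

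**Working it through.** **1. The plan's own figure.** Section 2.2 needs 105 and recruits 150 to allow for 30% loss: 105 / (1 − 0.30) = 150, and 150 × 0.70 = 105. This reproduces. (The 105 itself cannot be verified, because the number of measurements, their correlation and the effect tested are not stated. This point does not depend on it.)

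**2. Participants left out if all four values are required.** N = 150, times the loss rates in section 2.2:
- 3.4%: 150 × 0.034 = 5.1
- 12.3%: 150 × 0.123 = 18.5
- 16%: 150 × 0.16 = 24
- 30%: 150 × 0.30 = 45

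**3. Precision.** The documents give no correlations, so these are assumed. Correlations between BMI changes from baseline are 0.80 (post-treatment and 3 months), 0.70 (post-treatment and 6 months) and 0.85 (3 and 6 months). Dropout is assumed random and permanent. The variance of the 6-month difference using partial data, relative to completers only, is

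n6 × [ r² / n_post + (R² − r²) / n_3m + (1 − R²) / n6 ]

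with r² = 0.70² = 0.49 and R² = (0.49 + 0.7225 − 2 × 0.70 × 0.85 × 0.80) / (1 − 0.64) = 0.2605 / 0.36 = 0.7236.

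At 30% loss:
- Loss spread equally over three intervals: retention per interval is 0.70^(1/3) = 0.888, so n6/n_post = 0.788 and n6/n_3m = 0.888. Ratio = 0.49 × 0.788 + 0.2336 × 0.888 + 0.2764 = 0.870, a saving of 13.0%.
- Loss only after post-treatment: n6/n_post = 0.70 and n6/n_3m = 0.837. Ratio = 0.343 + 0.195 + 0.276 = 0.815 (before rounding the terms), a saving of 18.5%.

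| Loss | Variance saving |
|---|---|
| 3.4% | 1.4–2.1% |
| 12.3% | 5.1–7.5% |
| 16% | 6.7–9.8% |
| 30% | 13.0–18.5% |

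At 30% loss, 105 completers would be worth 105 / 0.870 = 121 to 105 / 0.815 = 129. With correlations of 0.60/0.45/0.70 the saving at 30% is 7.5–10.8%; with 0.90/0.82/0.93 it is 16.4–23.3%.

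**4. Bias, as illustration only.** Assumed SDs of BMI change are 0.7, 1.0, 1.3 and 1.5 kg/m² at week 5, post-treatment, 3 and 6 months. Assumed correlations of week-5 change with the later changes are 0.85, 0.68 and 0.60. Loss is spread over three intervals, and the log-odds of leaving rise by 0.5, 1.0 or 1.5 per SD of the last observed change.

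- *Mechanism in the usual-treatment arm only, no true difference.* The size of the completer bias at 6 months, experimental vs usual treatment, is 0.02–0.05 kg/m² at 3.4% loss, 0.07–0.17 at 12.3%, 0.09–0.22 at 16% and 0.17–0.40 at 30%. Its sign depends on whether those doing badly or well tend to leave.
- *Same mechanism in both arms, no true difference.* No bias.
- *Same mechanism in both arms, assumed true 6-month difference of 0.46 × 1.5 = 0.69 kg/m².* With 30% loss in the comparator arm, the completer difference shrinks by about 0.04, 0.09 and 0.14 kg/m² for the three strengths. At 16% the shrinkage is 0.01–0.08. These depend slightly on how the difference builds up: setting it at 0.46 SD at every visit gives 0.03, 0.08 and 0.13 at 30%.

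**The case against.** The strongest reply is that the plan never says complete cases. Promising ITT alongside per-protocol suggests that something wider than completers is intended. That is right: the defect is an unspecified method, not a wrong one chosen. It does not close the gap, because the one model named does not deliver ITT without an added step.

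Second, the allowance for loss is already built in. This also stands. A reader might infer that the trial is underpowered once dropouts are deleted. The documents do not support that, since 30% loss leaves exactly the 105 required. Moving to the equivalent of 121–129 is a gain, not the repair of a shortfall.

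Third, using four moments is no error. They match objective 1, and the week-5 BMI has its own planned use in comparing the impulsive and reflexive trainings. The weekly values are therefore useful extra information rather than a required part of the model. Their number is uncertain too: depending on where session 1 falls, there are 9, 10 or 11 BMI occasions.

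A reader might also take the session numbers as showing that baseline is undefined. Section 4 puts the pre value at session 1 and post-treatment at session 7. Section 3 has "Informative session (session 1; week 0", the pre-treatment assessment as session 2, session 7 as an intervention session and post-treatment as session 11. But section 2.4 does define a baseline: in "the week before the pre-treatment assessment session, it will be recorded daily to obtain the baseline weight and then averaged". The section 4 numbers would also fit a count of assessment and training sessions only. This is a labelling matter, separate from missing data.

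**Conclusion.** The point holds as a gap in specification that should be fixed. ITT is promised for the primary outcome, neither the set nor the handling of missing BMI is given, and the named ANOVA in its standard form would exclude 45 of 150 at the 30% loss allowed for, or about 5 to 24 at the cited rates.

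The size of the cost is conditional. The precision loss of 13–19% in variance at 30% loss (7.5–23% over other correlations) requires listwise deletion, random dropout and correlations that are not in the documents. Bias requires dropout that depends on outcome. Two stronger readings are tempting:
- *That completer results will be biased.* The documents do not show which mechanism applies.
- *That an equal mechanism in all arms costs only precision.* That is true only with no treatment effect; a real effect is shrunk.

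At 3.4%, the only 6-month attrition rate cited, both costs are small.

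**What to change.** In section 4:
- Define the ITT set as all randomised participants, analysed as allocated. Say how someone with no baseline or no later BMI is treated, and define the per-protocol set.
- Make the primary BMI analysis a likelihood-based mixed model for repeated measures using every available value at the four moments, with a named covariance structure and one fallback. Multiple imputation before the planned ANOVA is an acceptable alternative.
- Where practical, bring in the weekly and week-5 BMI already collected, as extra occasions or as auxiliary data.
- Report experimental vs sham and experimental vs usual treatment at post-treatment, 3 and 6 months.
- State the missing-at-random assumption, add one missing-not-at-random sensitivity analysis (for example, delta-adjusted by arm), and keep the completer ANOVA as secondary.

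Separately, reconcile the session numbers in section 4 with section 3, and confirm that the averaged baseline weight in section 2.4 is the pre value.

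The cost is SAP wording and some analyst time, with no new visits or data. The downsides are that the primary result then relies on missing-at-random, a covariance structure has to be fixed in advance, and one more analysis must be reported.

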People between 18 and 55 years old will be candidates to participate in the study, with a good command of the Spanish language, a range of BMI between 25 and 39.9 kg/m², and with at least two electronic devices available (one tablet, computer or smartphone to attend the online meeting and one smartphone with a gyroscope to do the training with the apps). All candidates will be screened for medical and psychological disorders and excluded if they have: (i) traumatic, digestive, metabolic or systemic disorders that affect the central nervous system, autonomic or endocrine, (ii) cardiovascular or any other disorders that prevent physical exercise; (iii) psychopathological disorders or presence of severe symptoms in the Depression Anxiety and Stress Scale-21 (DASS-21); (iv) eating disorders or presence of criteria in the Questionnaire on Eating and Weight Patterns-5 (QEWP-5); (v) pharmacological or any other kind of treatment for losing weight at present; (vi) candidates for bariatric surgery; (vii) food conditions that could interfere with the stimulus of the program (allergies, sprue, vegetarianism, veganism); (viii) current pregnancy or breastfeeding (or expected pregnancy in the following six months); (ix) weight loss $>5\%$ on the 3 months previous to the program; (x) use of medication that affects weight; (xi) frequent use of alcohol or other drugs that affects food intake.

Sampling context:

The recruitment will be carried out through social media and the web of the project.

Randomization and blinding:

A randomization (minimization) through the software Minimizer® will be performed to avoid imbalances between the groups in age, sex, and BMI (Stout et al., 1994). The psychologists that conduct the assessments (screening, evaluation sessions and follow-ups) will be blinded to the group allocation during the whole project. Moreover, since all assessments will be computerized and online, they are not subject to the biases of the evaluator. Further, all participants will be blind to their condition. Also, the people who perform the statistical analyses will be blind to the condition of the groups, through the coding of the interventions. Only the therapist performing the interventions will not be blind to the allocation of the participants.

2.3. Interventions:

Pre-treatment interventions (all groups).

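### Arms are minimised on age, sex and BMI, but the planned ANOVA has no covariates and uses the pre-treatment value only as a time level, so precision is lost to the extent that these predict change

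*Combined protocol and SAP*

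**What the plan says.** - **Allocation** (section 2.2, Randomization and blinding): a minimisation procedure "will be performed to avoid imbalances between the groups in age, sex, and BMI".
- **Model** (section 4, Data analysis plan): "Models of repeated measures two-way ANOVA will be performed, using as dependent variables (DV". The list that follows contains outcomes and no covariates. For objective 1 the outcome is change in BMI over four moments, the first of which is pre-treatment. The between-group effect size is likewise a difference in change from the first measurement, scaled by the pooled SD at that time.
- **Allocation factors in the analysis** (section 4): age is not mentioned. Sex and weight class appear only as a separate look at whether outcomes differ by them. No ANOVA term is named as the primary test.
- **Sample size** (section 2.2): derived "considering the statistical method (models of repeated measures inter and intra subjects"), "assuming an alpha level of 0.05 and a power of 0.80"; "the resulting sample size calculated with G-Power was 105 participants". This was raised to 150 so that "the study could suffer a sample loss of 30% from the initial session to the follow-up at 6 months" without falling short of the power target.

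**The concern.** Minimisation suppresses the chance differences between arms in age, sex and BMI. If those factors predict the outcome being tested, an unadjusted model keeps their variation in the error term although the design has largely removed it from the between-arm comparison. The standard error is then too wide and the true type I error falls below the nominal 0.05.

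Separately, entering the pre-treatment value as a level of time makes the group-by-time test a comparison of changes. With equal pre and post variances, that is less precise than using the pre value as a covariate whenever the pre-to-follow-up correlation is below 1. What is at stake is power that the same participants could provide. Bias and excess false positives are not in question.

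**Working it through.** **1. The plan's own figure.** The attrition step checks: 150 × 0.70 = 105. The 105 itself cannot be tested from the stated inputs, because the number of measurements (m) and their correlation (ρ) are missing. Assume f = d/2 = 0.46/2 = 0.23 and m = 4. The between-factors test has noncentrality f²·N·m/(1+(m−1)ρ). At ρ = 0.41 and N = 105 this is 0.0529 × 105 × 4 / 2.23 = 9.96, and the required N is 105. At ρ = 0.5 the required N is 117, and power at 105 is 75.2%. The within-between interaction at ρ = 0.5 needs 36. So 105 is reachable with an unstated correlation, and I do not call it wrong.

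**2. Omitting the minimisation factors.** Assumptions not in the documents: biased-coin minimisation (probability 0.8) on sex, three age bands and three BMI bands; R², the share of change explained by these factors; and an effect giving about 80% unadjusted power. The simulation used N = 105, three arms, 3,000 runs per cell and an F test of arm with and without the factors. Ranges span repeat simulations; a dash means no figure is available.

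| R² | Type I unadjusted | Type I adjusted | Power unadjusted | Power adjusted |
|---|---|---|---|---|
| 1% | 5.4% | – | 79.1% | 79.5% |
| 2% | 5.1% | – | 79.7% | 80.0% |
| 5% | 4.5–4.6% | 5.0% | 79.2–80% | 80.7–82% |
| 10% | 3.4–4.1% | 5.1–5.4% | 79.5–81% | 83.8–85% |
| 20% | 2.1–2.5% | 4.6–4.7% | 81–81.5% | 88–88.8% |

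The Monte Carlo standard error is about √(0.05 × 0.95/3000) = 0.4 points for type I error and √(0.8 × 0.2/3000) = 0.7 points for power. I therefore round the gains to 2 points or fewer at R² of 5% or less, 4 to 5 at 10%, and about 7 at 20%. The simulation tests a single outcome. It is not the full four-moment ANOVA.

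**3. Using the pre value as a time level.** Let ρ now be the pre-to-follow-up correlation, with equal pre and post variance σ².

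- Variance of change: 2σ²(1−ρ).
- Residual variance after adjusting for the pre value: σ²(1−ρ²).
- Ratio: (1+ρ)/2.

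For a contrast with 80% power as a change score, adjusted power is Φ(2.802/√ratio − 1.960). At ρ = 0.7 this is Φ(2.802 × 1.0847 − 1.960) = Φ(1.079) = 86.0%.

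| ρ (assumed) | Variance ratio | Power after adjustment |
|---|---|---|
| 0.97 | 0.985 | 80.6% |
| 0.95 | 0.975 | 81.0% |
| 0.90 | 0.950 | 82.0% |
| 0.80 | 0.900 | 84.0% |
| 0.70 | 0.850 | 86.0% |
| 0.50 | 0.750 | 89.9% |

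A simulation of the minimised design at N = 105 agrees. Change-score against baseline-adjusted power was 82.5/90.1% at ρ = 0.5, 82.1/84.4% at 0.8, 82.6/82.6% at 0.95 and 81.9/81.7% at 0.98. Type I error of the change analysis was 3.3%, 5.1%, 5.4% and 4.7% in turn, so it was clearly conservative only at ρ = 0.5.

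**4. Overlap for BMI.** Pre-treatment BMI is both an allocation factor and the baseline of the primary outcome, so the gains in steps 2 and 3 overlap. On the formula above, pre-treatment BMI explains (1−ρ)/2 of change: 1.5% at ρ = 0.97 and 5% at 0.90. To reach R² = 10%, age and sex would have to add 5 to 8.5 points; to reach 20%, 15 to 18.5 points.

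**The case against.** The strongest reply is that a group-by-time test on change is a recognised and valid analysis. It already removes each participant's stable level, including the stable effects of age, sex and starting BMI; only their relation to change remains in the error. For BMI, where a high correlation is plausible, the baseline gain is about 2 points or fewer. An R² of 10–20% would require age and sex to predict BMI change to a degree that nothing in the documents supports. Simulated unadjusted power stays close to the 0.80 target even at 105, which is the floor after 30% loss. Section 2.2 cites attrition of 3.4–16% in earlier studies, and at the full 150 simulated power is 92–93% unadjusted against 92–96% adjusted.

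Most of this stands. It limits the size of the point without removing it: nothing else in the documents supplies the adjustment, the cost is trivial, and task, diary and rating-scale outcomes could have correlations low enough for the gain to matter.

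A reader might go further and infer that power is lost on every outcome, or that the BMI test certainly runs below 0.05. The documents support neither, since both depend on unstated R² and correlations and the effect largely vanishes at low R². A reader might also infer that the pre-treatment value is ignored; it is not, because it is a level of time. Finally, because no term is named, a reader might suppose that the group main effect is the primary test. In a four-moment simulation its power was 74.7%, 26.9% and 8.9% at ρ = 0.5, 0.8 and 0.95, against about 83% for group by time. Section 4 defines the BMI outcome as change, which points to group by time, so this is a reason to name the contrast and not a finding of low power.

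**Conclusion.** The point holds as a matter of precision. The named model leaves out the allocation factors and does not use the pre-treatment value as a covariate. Standard errors are wider than necessary, and the test mildly conservative, only in so far as age, sex or the pre value predict change.

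For BMI the loss is probably small: a 1.5–5% variance saving from baseline adjustment at ρ of 0.97–0.90, with more only if age and sex also predict BMI change. The material gains, about 6 to 10 power points, are confined to outcomes with ρ of about 0.7–0.5. All these sizes rest on assumed R² and ρ, and on equal pre and post variances. The validity of the planned test is not in doubt, and the trial is not shown to be underpowered.

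**What to change.** In section 4:

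- **BMI:** model the post-treatment, 3-month and 6-month values with group, time, group by time, pre-treatment BMI, age and sex, each covariate also by time. Pre-treatment BMI enters once, serving as both baseline and allocation factor. Name the group contrast that is the primary test.
- **Secondary outcomes:** model whichever post-baseline values are collected, adjusting for the outcome's own pre value where one exists, plus age, sex and pre-treatment BMI. A single three-time-point form will not fit all of them. Approach-avoidance bias and food inhibition are measured before and after one week of training, the Now or Later questionnaire is pre and post only (section 2.4), and food choice, food liking and MEDAS are not in the follow-up battery (section 3, item 8).
- **Adherence to diet and exercise:** the guidelines are issued in week 2, after the week 1 pre-treatment assessment, so there is no pre value. Adjust for age, sex and pre-treatment BMI only.

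The cost is a change to the analysis text and a few error degrees of freedom. No new data are needed. If the covariates turn out not to predict change, almost nothing is lost.
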